12. CONCOMITANT MEDICATIONS

In addition to the procedural medications described in the sections below, reportable medications to be recorded in the electronic Case Report Form (eCRF) are medications taken by the subject to treat their cardiovascular disease, including antithrombotics (antiplatelets, anticoagulants), antibiotics, NSAIDs, steroids, diuretics, calcium channel blockers, and statins. These medications will be captured at baseline through study completion and include prior ongoing or new use of the medications mentioned in this section (either prescription or over the counter).

In addition, all COVID-19 vaccinations received (prior to or after enrollment) will be recorded in the eCRF.

The following antiplatelet and anticoagulation regimen described in **Sections 12.1, 12.2, and 12.3** below, is required, unless otherwise dictated by Institution or PI standard of care. If an alternative antiplatelet and anticoagulation regimen is required per Institution or PI, the regimen must be documented prior to the first subject being enrolled. This alternative antiplatelet and anticoagulation regimen will be used to monitor pre-procedure, peri-procedure, and post-procedure medication compliance. Non-compliance with the documented antiplatelet and anticoagulation regimen will be considered a protocol deviation. If non-compliance is deemed medically necessary for the patient's safety and/or well-being, the reason must be documented, and the non-compliance will not be considered a protocol deviation.

12.1. Pre-Procedural Medications

Pre-procedural anticoagulation should be stopped if required by the PI or Institution.

Subjects taking warfarin prior to the index procedure with a pre-procedural INR >2 due to coagulopathy (on the day of the index procedure) are still eligible for study device treatment subject to the approval of the PI. Subjects on antiplatelet therapy should stop, if required by the Institution or PI.

12.2. Peri-Procedural Medications

Full therapeutic anticoagulation is required for all subjects for the duration of the index procedure. The anticoagulation regimen should follow the site's standard anticoagulation protocol and must be documented in the subject's study records.

12.3. Post-Procedural Medications

For all subjects, institute full anticoagulation within 4 hours following the completed index procedure and follow the below regimen. Start time of full anticoagulation should be documented.

Enoxaparin for the first 30 days post-procedure. After this time, continue full anticoagulation with an oral anticoagulant. If warfarin is used, an INR of 2.0-3.0 with appropriate bridging therapy is required. A direct oral anticoagulant, such as apixaban, dabigatran, rivaroxaban, or edoxaban can be used instead of warfarin.

The minimum anticoagulation treatment durations are:

- 3 months for nonthrombotic subjects
- 12 months for thrombotic subjects
- Long-term for subjects with thrombophilia

Concomitant antiplatelet therapy with aspirin or thienopyridine class drugs may also be used at the discretion of the PI. Due to the high risk of bleeding, dual antiplatelet therapy in addition to anticoagulation is not recommended unless deemed appropriate by the PI. Antiplatelet therapy can be considered after anticoagulation therapy is discontinued.

13. INDEX PROCEDURE

All imaging-related inclusion/exclusion criteria are based on the PI's assessment at the time of the Index Procedure.

13.1. Index Procedure Baseline IVUS

Final eligibility of all subjects will be confirmed using the Index Procedure Baseline IVUS. The Index Procedure Baseline IVUS must be performed during the index procedure in order to assess baseline imaging-related eligibility for inclusion as described in **Section 13.1.3** below. Both the baseline venogram and IVUS are to be performed as per guidelines established by the independent core laboratory. Baseline venograms performed for all enrolled subjects will be reviewed by the core laboratory as outlined in the venographic core laboratory protocol.

All data that are required to be recorded during the index procedure are reflected in the index procedure interval eCRFs within the EDC. Required measurements and data listed in the following sections are not exhaustive of all data that is required. Therefore, the required data should be reviewed in advance of the procedure to ensure it is understood and captured appropriately. The electronic Case Report Form (eCRF) Completion Guidelines contain instructions for data entry and should be referenced, as necessary.

13.1.1. Preparation

Procedural techniques will be in accordance with the institutional standard of care for iliofemoral venoplasty and stenting.

All subjects should receive the appropriate anticoagulant therapy per **Section 12**.

13.1.2. IVC Filter Placement

IVC filter placement is not recommended but is ultimately at the discretion of the PI in circumstances such as floating thrombus in ilio caval segments or if there is planned use of mechanical thrombectomy in the presence of acute thrombus. In all cases, the IVC filter should be removed as soon as deemed safe by the PI. Confirmation of successful placement and removal of the IVC filter should be documented in the source documents and the eCRF.

13.1.3. Baseline Venographic and IVUS Requirements

Baseline venographic and IVUS measurements of the target lesion and target vessels (visual estimate) shall be captured to determine eligibility and include, but are not limited to, the following:

- Target lesion(s) details including vessel location(s), lesion length(s), and pre-PTA % reduction in target vessel lumen diameter
- Indication for stenting and final disease state classification (acute DVT, nonthrombotic, chronic postthrombotic)
- Reference vessel diameter(s)

- Inflow venous patency (if patency of profunda cannot be confirmed by venogram or IVUS, pre-operative DUS findings may be used to confirm)
- Absence of thrombus and/or successfully treated thrombus for acute DVT subjects

13.2. **Pre-Dilation**

Please refer to the Instructions for Use (IFU) for detailed instructions regarding Pre-dilation inflation recommendations. It is recommended that pre-dilation equivalent to the size of the intended stent be performed.

Pre-dilation balloon-related details will be recorded and include, but are not limited to, the following: balloon name/manufacturer and balloon size, max pressure, inflation duration at max pressure, and max inflation diameter across all inflations.

13.3. **Study Device Treatment**

Subjects who meet all inclusion criteria, and who do not meet any exclusion criteria will be deemed eligible for Study Device Treatment.

13.3.1. **Enrollment (Intent-to-Treat)**

A subject is defined as intent-to-treat (ITT) and officially enrolled in the study once the DUO Venous Stent System is advanced through the introducer sheath.

Subjects in whom no DUO Stent implant is placed will be exited after 30 days. Subjects in whom at least one DUO Stent implant is placed will be followed for 36 months.

The per-protocol (PP) population will be defined as ITT subjects with evaluable data that have met the definition for device success, excluding subjects with major deviations, such as those who meet criteria for a protocol violation(s), as determined by the Sponsor.

13.3.2. **Treatment Recommendations**

Please refer to the IFU for detailed instructions regarding recommended criteria for use of the study device and stent sizing. IVUS is required for stent sizing.

NOTE: When overlapping study devices, there should be no more than 2mm of diameter difference between devices.

13.3.3. **Post-Study Device Treatment Measurements**

The following information should be recorded Post-Study Device Treatment:

- Assessment of successful introduction, deployment, and withdrawal with the stent remaining in the intended location through completion of the procedure
- Number and type of DUO Venous Stent Systems used to treat subject and associated lot number(s) as well as number of stents deployed

- Vessel location and size of each deployed DUO Stent

13.3.4. **Final Treatment Results**

The following information should be recorded after post-dilation and upon completion of index procedure and includes but is not limited to:

- Adjunctive procedures performed and outcomes
- Study Device Procedure Time (defined as the time the first DUO Venous Stent System is advanced through the introducer sheath to the time of withdrawal of the last balloon catheter)
- Adverse event/device event occurrence

14. POST-PROCEDURE/PRE-DISCHARGE

All subjects will be assessed post-procedure prior to discharge (Pre-Discharge) and shall receive a medical regimen for the medications required post-procedure per **Section 12**. All study medications shall be captured in the eCRF.

14.1. Required Assessments

Assessments required post-procedure/pre-discharge include the following:

- Adverse event assessment
- Concomitant medication review
- PT/INR (only for subjects on chronic warfarin)*
- aPTT (only for subjects on chronic heparin)*

* If a subject is on chronic warfarin or chronic heparin, they may be discharged before lab results from PT/INR or aPTT tests are obtained.

All subjects receiving treatment with a DUO Stent implant should be provided with the DUO Stent System Subject Implant Card (PIC). The PIC is designed for the subject to carry along with their insurance cards. This PIC is to be completed by the designated research personnel to include information pertaining to the DUO Stent(s) including the model, lot number and vessel location of the implanted DUO Stent(s) and the date of the index procedure. The card also provides manufacturer information and MRI Compatibility.

15. REQUIRED FOLLOW-UP VISITS AND ASSESSMENTS

All subjects will be required to return for clinic follow-up visits as outlined in **Section 8.1** and in the sections below.

In the event of a public health crisis, a global pandemic, a natural disaster, or any other event which would preclude research sites from conducting research or restrict subjects' ability to attend follow-up visits, guidance will be provided by the Sponsor regarding visit windows.

15.1. 30-day Follow-up Visit (-2 days / +14 days post-Index Procedure)

The following assessments are required to be performed at the 30-day follow-up visit:

- SARS-CoV-2 Testing (if required per Section 9.2)
- DUS
- Venous Ulcer Assessment
- Adverse event assessment
- Review of concomitant medications

15.2. 6-month Follow-up Visit (±30 days post-Index Procedure)

The following assessments are required to be performed at the 6-month follow-up visit:

- SARS-CoV-2 Testing (if required per Section 9.2)
- Venous Ulcer Assessment
- CEAP Classification
- Villalta Score
- VCSS Pain Score
- DUS
- VEINES-QOL/Sym Questionnaire
- EQ-5D-3L Questionnaire
- Adverse event assessment
- Review of concomitant medications

15.3. 12-month Follow-up Visit (±30 days post-Index Procedure)

The following assessments are required to be performed at the 12-month follow-up visit:

- SARS-CoV-2 Testing (if required per Section 9.2)
- Venous Ulcer Assessment
- CEAP Classification

- Villalta Score
- VCSS Pain Score
- DUS
- X-ray of implanted stent(s)
- VEINES-QOL/Sym Questionnaire
- EQ-5D-3L Questionnaire
- Adverse event assessment
- Review of concomitant medications
- Follow-up venogram and IVUS are required if DUS suggests >50% stenosis or occlusion of the stented segment, or if the DUS is non-diagnostic or sub-optimal (i.e., due to obesity). If a follow-up venogram/IVUS is refused by the subject, this must be documented and will not be considered a protocol deviation and the DUS will be used if available.

15.4. **24-month Follow-up Visit (\pm 30 days post-Index Procedure)**

The following assessments are required to be performed at the 24-month follow-up visit:

- SARS-CoV-2 Testing (if required per Section 9.2)
- DUS
- X-ray of implanted stent(s)
- Venous Ulcer Assessment
- CEAP Classification
- Villalta Score
- VCSS Pain Score
- VEINES-QOL/Sym Questionnaire
- EQ-5D-3L Questionnaire
- Adverse event assessment
- Review of concomitant medications
- Follow-up venogram and IVUS may be required if DUS suggests >50% stenosis or occlusion of the stented segment, **and** if the subject is symptomatic requiring a reintervention. If a follow-up venogram and/or IVUS is refused by the subject, this must be documented and will not be considered a protocol deviation and the DUS will be used if available.

15.5. 36-month Follow-up Visit (\pm 30 days post-Index Procedure)

The following assessments are required to be performed at the 36-month follow-up visit:

- SARS-CoV-2 Testing (if required per Section 9.2)
- DUS
- X-ray of implanted stent(s)
- Venous Ulcer Assessment
- CEAP Classification
- Villalta Score
- VCSS Pain Score
- VEINES-QOL/Sym Questionnaire
- EQ-5D-3L Questionnaire
- Adverse event assessment
- Review of concomitant medications
- Follow-up venogram and IVUS may be required if DUS suggests >50% stenosis or occlusion of the stented segment, **and** if the subject is symptomatic requiring a reintervention. If a follow-up venogram and/or IVUS is refused by the subject, this must be documented and will not be considered a protocol deviation and the DUS will be used if available.

There is no follow-up or observation planned after the subject completes the 36-month follow-up visit and is exited from the study.

15.6. Unscheduled Visit

An Unscheduled visit will be documented when a subject presents to the hospital or clinic between study-required follow-up visits and is seen by study personnel for a limb-related event, including reinterventions. The assessments below should be performed prior to any interventional procedures to the target limb. In addition, all imaging studies performed should follow the guidelines set forth by the respective core laboratory. This imaging should be submitted to the respective core laboratories within 3 business days for review and analysis.

- SARS-CoV-2 Testing (if required per Section 9.2)
- Venous Ulcer Assessment (if applicable)
- CEAP Classification
- Villalta Score

- VCSS Pain Score
- VEINES-QOL/SYM Questionnaire
- EQ-5D-3L Questionnaire
- DUS (as clinically indicated)
- Venogram and/or IVUS (as clinically indicated)
- X-ray assessment (as clinically indicated)
- Adverse event assessment
- Review of concomitant medications

Note: Any change in concomitant medications, including any loading dose provided during an unscheduled procedure, should be recorded in the eCRF.

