⁴ If a SARS-CoV-2 test is unavailable due to institution policy, a test shortage, or if there is a delay in test results, the subject must complete the COVID-19 questionnaire and answer NO to all questions to be eligible for study treatment. If a SARS-CoV-2 test is unavailable due to institution policy or a test shortage at the time of any follow-up or unscheduled visits, the COVID-19 questionnaire must be completed. A SARS-CoV-2 test will not be required if a subject has received a complete cycle of an authorized COVID-19 vaccine or has documented evidence of a positive COVID-19 antibody test, is asymptomatic, and has no long-lasting effects (per PI discretion) from a prior COVID-19 infection.

⁵ PT/INR to be obtained only if a subject is on chronic warfarin therapy.

⁶ aPTT to be obtained only if a subject is on chronic heparin therapy.

⁷ Negative urine or blood pregnancy test is required for female subjects of childbearing potential within 7 days of the index procedure.

⁸ All scheduled DUS exams should be performed per the protocol established by the core laboratory. If a DUS is non-diagnostic (per the imaging protocol), the site should make every effort to obtain a repeat exam within the visit window.

⁹ Unscheduled tests and assessments should be completed prior to any interventional procedures to target limb.

¹⁰ Unscheduled tests and assessments to be performed as clinically indicated.

¹¹ All imaging of the target limb acquired during scheduled visits or an interventional procedure to the target limb (such as venogram, IVUS, DUS, or X-ray) should be submitted to the respective core laboratory within 3 business days.

¹² Required if DUS suggests >50% stenosis or occlusion of the stented segment, or if the DUS is non-diagnostic or sub-optimal (i.e., due to obesity). If a follow-up venogram and/or IVUS is refused by the subject, this must be documented and will not be considered a protocol deviation.

¹³ For the purposes of this study, all AEs, regardless of relatedness to the study device and/or study device procedure, target limb, or underlying venous disease are required to be reported on the AE eCRF and are considered “protocol reportable”. Please see **Section 17** for more information on safety events and reporting requirements.

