¹⁴ Follow-up assessments (required at the 30-day visit and beyond) that cannot be performed due to a subject’s medical condition (i.e., amputation) will not be considered protocol deviations if documentation of the medical condition is present in the subject’s medical records.

¹⁵ To be performed both pre-and post-study device treatment as outlined in **Sections 9.5** and **9.6** and as described in the core laboratory manuals.

¹⁶ May be required if DUS suggests >50% restenosis or occlusion of the stented segment **and** if the subject is presently symptomatic requiring a reintervention. If a follow-up venogram and/or IVUS is refused by the subject, this must be documented and will not be considered a protocol deviation.

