9. REQUIRED TESTS AND ASSESSMENTS

The tests and assessments described in this section are required at baseline and/or at various follow-up visits according to the Time and Events Schedule in **Section 8.1**.

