IVUS is required at the index procedure, for any reinterventions, and if the 12-month site reported or core laboratory adjudicated DUS shows >50% stenosis or occlusion of the stented segment. In addition, IVUS may be required for the 24 or 36-month DUS shows >50% stenosis or occlusion of the stented segment **and** the subject is symptomatic requiring a reintervention. Operators will be trained on the IVUS protocol provided by the core laboratory. No test cases are required for IVUS. A comprehensive overview for IVUS acquisition requirements can be found in the core laboratory manual.

9.6. **Venographic Imaging**

Venography is an important modality for the assessment and treatment of iliofemoral compression syndrome. A lower extremity vein caudal to the lesion, typically the popliteal vein or mid femoral vein, is accessed and radiopaque iodinated contrast is injected. Images are then captured as the dye flows cranially under digital subtraction angiography (DSA). This allows for the assessment of stenosis of the veins from extrinsic compression/obstruction, and for the detection of acute thrombus and intrinsic vein defects (webbing, spurs, etc.). Angiographic images are typically acquired in the AP view. However, angulated views from the LAO or RAO projections are essential to add additional information about vessel narrowing or “pancaking”, especially when the stenosis is eccentric. This is also useful if the AP view does not demonstrate a narrowing of the vessel. A lack of dye in a venous segment usually represents an occlusion. In the presence of occlusion there are typically numerous collaterals clearly visualized on venography.

A full venographic run of the IVC, CIV, EIV, and CFV must be acquired both pre-treatment and post-treatment. For all venography runs, a radiopaque or marker pigtail catheter should be utilized. This allows for accurate lesion length determination by the core laboratory. Images must be acquired in DICOM format with and without DSA. Full venographic runs, not only still frames, are required for core laboratory assessment.

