19.11. Primary Efficacy Objective

Subjects Included the Analysis: Subjects who meet the ITT definition.

Efficacy: Primary patency of stented segment (confirmed by core laboratory) at 12 months evaluated per subject.

Hypothesis:

H_0 : Proportion of subjects with primary patency (p_{p_pat}) is less than or equal to performance goal (PG) at 12 months, $p_{p_pat} \leq PG$

H_1 : Proportion of subjects with primary patency is greater than the performance goal at 12 months, $p_{p_pat} > PG$

The primary patency proportion will be calculated such that the numerator is the number of subjects found to be patent at 12 months. The denominator is the total number of subjects found to be patent or not patent at 12 months.

Patency is:

- An in-window patent stenosis assessment with no reintervention per definition prior to the close of the 12-month window.
- In the absence of an in-window stenosis assessment, a subsequent patent stenosis assessment with no prior reintervention per definition can be used to declare patency at 12 months.

Lack of patency is:

- A reintervention per definition prior to the close of the 12-month visit window.
- A non-patent stenosis assessment within the 12-month visit window.

Performance Goal: The PG for primary efficacy will be set when all enrolled subjects complete the index procedure of this pivotal IDE trial based upon the proportions of ITT subjects in each of the disease states, i.e. nonthrombotic (p_{NT_ENROLL}), acute thrombotic (p_{AT_ENROLL}) and chronic postthrombotic (p_{CPT_ENROLL}). The disease state specific PGs were adopted as suggested in Razavi et al¹ that is, the lower 95% confidence limit minus 0.10. The disease state PGs are .83, .70 and .66 for nonthrombotic, acute thrombotic and chronic postthrombotic subjects respectively. The PG for the

pivotal study will be a weighted combination of these disease state specific PGs, where the weights are the proportion of subjects in each disease state in the ITT sample, i.e. study PG = $(p_{NT_ENROLL}) * 0.83 + (p_{AT_ENROLL}) * .70 + (p_{CPT_ENROLL}) * 0.66$. The same PG will be used overall and in the SARS-CoV-2 negative subgroup. In order to have a minimum number of subjects from each disease condition in the ITT sample, the study will require that at least 20% of the ITT subjects are in each of the disease state.

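### IVUS at reintervention is mandatory in Section 9.5 but optional in Section 15.6, and a subject reintervened on without IVUS before the 12-month window closes can count as patent

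*Combined protocol and SAP*

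**What the plan says.** **When IVUS is required.** Section 9.5 states that "IVUS is required at the index procedure, for any reinterventions", and Section 9.6 sets the same rule for venography. Under Section 17.8, a required test that is not done is a protocol deviation.

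Section 15.6 governs unscheduled limb-related visits, names reinterventions among them, and lists what to do before any intervention on the target limb. Its imaging entry is "Venogram and/or IVUS (as clinically indicated". Footnote 10 of the Section 8.1 schedule reads: "Unscheduled tests and assessments to be performed as clinically indicated". The opening of Section 9 says its tests "are required at baseline and/or at various follow-up visits according to the Time and Events Schedule".

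For 24 and 36 months, Sections 15.4 and 15.5 say "Follow-up venogram and IVUS may be required if DUS suggests >50% stenosis or occlusion of the stented segment", and footnote 16 adds the condition "if the subject is presently symptomatic requiring a reintervention". The matching sentence in Section 9.5 is equally permissive.

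**How the endpoint uses it.** Sections 6.1 and 23 define CD-TLR as a procedure for new, recurrent or worsening symptoms, with stenosis above 50% or occlusion in the stented segment confirmed by diagnostic IVUS. Section 19.11 defines patency as "An in-window patent stenosis assessment with no reintervention per definition prior to the close of the 12-month window". Loss of patency is either a reintervention meeting the definition before that window closes, or "A non-patent stenosis assessment within the 12-month visit window".

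**The concern.** Two sections give different instructions for the same procedure, and the endpoint depends on which one a site follows. If the operator omits IVUS, a symptomatic in-stent reintervention cannot be a CD-TLR. If it happens before the 12-month window closes and the reopened stent looks open at 12 months, the subject moves from failure to success in the primary efficacy endpoint. After that window, only the observational CD-TLR rate through 36 months is lowered.

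Omitting IVUS can remove a failure but never create one. The trial is single-arm and unblinded against a fixed goal, so no control group offsets the error, and the person choosing the imaging is treating the patient.

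**Working it through.** **1. Tracing one subject through the rules.** The stent occludes at month 5 with symptoms, is reopened on venography without IVUS, and is open on the 12-month duplex.

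- Is it a CD-TLR (Sections 6.1, 23)? No: there is no IVUS confirmation.
- Is it a reintervention under the Section 19.11 definition? No, since that definition is CD-TLR.
- Is there a non-patent assessment inside the 12-month window? No: the occlusion was seen at month 5.
- Is there an in-window patent assessment and no qualifying reintervention? Yes. The subject is **primary-patent**.

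The same subject also fits the description of secondary patency in Section 6.2 (open after reintervention for total occlusion), which cannot be intended.

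**2. Would another planned analysis catch it?** The best-case, worst-case and tipping-point analyses (Section 19.7) concern missing data, and this subject is not missing. The supportive Kaplan-Meier analysis uses the same event definition. The fallback to duplex when IVUS is refused is written only for the 12-, 24- and 36-month visits. CD-TVR does not need IVUS, so it can record the event, but it is observational and not part of primary patency.

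**3. Reproducing the plan's power.** Inputs from Section 19.11: N = 128, goals 0.83/0.70/0.66, assumed patency 0.96/0.87/0.79 (NT/AT/CPT), rejection at Z > 1.96 with null variance. An exact calculation for 43/43/42 subjects gives 98.5%, against 98% stated for equal thirds.

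**4. Effect of one uncounted event.** Taking analysis-set shares w equal to enrolled shares, the Section 19.11 variance reduces to

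SE = √[Σ wᵢ·PGᵢ·(1 − PGᵢ) / 128].

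For equal thirds:

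- Σ = (0.1411 + 0.2100 + 0.2244)/3 = 0.19183, so SE = √(0.19183/128) = 0.0387
- Threshold = 0.73 + 1.96 × 0.0387 = 0.8059, or 103.15 of 128
- 104/128 = 0.8125: Z = 2.13, two-sided p = 0.033
- 103/128 = 0.8047: Z = 1.93, two-sided p = 0.054
- One event: 1/128 = 0.78 percentage points; change in Z = 0.0078/0.0387 = 0.20

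| Mix NT/AT/CPT | PG | SE | Minimum patent to pass | Z per event |
|---|---|---|---|---|
| 20/20/60 | 0.702 | 0.0400 | 100 | 0.195 |
| Equal thirds | 0.730 | 0.0387 | 104 | 0.202 |
| 60/20/20 | 0.770 | 0.0366 | 108 | 0.213 |

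The first and last rows are the extremes over the ten mixes in the plan's table. For CD-TLR, one lost event is 1/160 = 0.63 percentage points of those enrolled.

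**5. Illustration only.** Suppose a fraction m of true failures is counted as patent by this route. The documents give no value for m. With true patency at the goals, exact one-sided type I error is:

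| Mix | m = 0 | 5% | 10% | 20% |
|---|---|---|---|---|
| Equal thirds | 1.9% | 4.2% | 8.4% | 25% |
| 20/20/60 | 2.8% | 6.1% | 12.1% | 34% |
| 60/20/20 | 2.5% | 5.0% | 9.1% | 25% |

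For equal thirds, m = 5% is about 1.7 subjects (0.05 × 128 × (1 − 0.7305), the goal at 43/43/42).

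**The case against.** The strongest reply is that the requirement already exists. Section 9.5 is the specific rule for reinterventions. Section 15.6 is a general list for all unscheduled visits, many of which lead to no intervention, so on ordinary reading Section 9.5 governs and a missed IVUS is a recorded deviation. That reading is available, but Section 15.6 names reinterventions itself, and Section 9 refers the reader to the schedule whose footnote 10 is permissive. Even if Section 9.5 controls, a deviation record does not change the classification: Section 19.11 still counts the subject as patent.

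The 24- and 36-month wording cannot touch the primary endpoint. That is correct; it bears only on observational CD-TLR. The relevant sentence in Section 9.5 opens as an addition to the general rule and may not weaken it.

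The boundary example is chosen at the edge, where one event decides any binary endpoint. Under the planning assumptions for equal thirds, the expected count is about 112 (Z about 3.7), eight above the minimum. The exact probability of landing on 103 is 0.7% under those assumptions and 1.3% at the goals. This stands, and it limits the urgency.

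The event would also be visible elsewhere: as an adverse event, possibly as in-stent thrombus among the MAEs, as CD-TVR, or under secondary patency. True, but none of these corrects primary patency. The CEC charter and core laboratory manual are not available here and may address missing IVUS, but neither could override the written definition.

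**Conclusion.** The concern holds. The IVUS instructions conflict, and the endpoint rules turn an omitted IVUS into a result favourable to the device, with no planned analysis to reveal it. For the primary endpoint this needs three conditions: IVUS is skipped, the reintervention precedes the close of the 12-month window, and the qualifying assessment is patent (in-window, or a later one if none is in window).

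The per-event effect is firm, given analysis-set shares equal to enrolled shares. The number of events is unknown, and the type I error figures rest on an assumed misclassification fraction. The 104-versus-103 contrast is for the all-subjects test at 1.96. Under the Hochberg rule, p = 0.033 suffices only if the SARS-CoV-2 negative subset also reaches p < 0.05. If the device performs as planned, a single event is unlikely to decide the trial. The point should be corrected because the fix is cheap and the bias has one direction.

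**What to change.** State in Sections 15.4, 15.5 and 15.6, footnotes 10 and 16, and the 24/36-month sentence of Section 9.5 that IVUS is required before any target-lesion reintervention, scheduled or not, through 36 months, with omission recorded as a deviation.

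Keep the IVUS-based CD-TLR definition and the primary endpoint unchanged. Report the number of symptomatic in-stent reinterventions lacking IVUS. Add one sensitivity analysis in which those with core-laboratory venographic stenosis above 50% or occlusion count as CD-TLR and, if they occur before the 12-month window closes, as loss of primary patency.

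The cost is one amendment with IRB/EC approval (Section 20.3) and one extra analysis. No procedure is added: Sections 9.5 and 9.6 already call for both images at reintervention, and the images already go to the core laboratory. The sponsor accepts more recorded deviations and a sensitivity result that may be less favourable.
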